mRNA	Messenger Ribonucleic Acid
NTS	Nucleus of the Solitary Tract
OCDS	Obsessive Compulsive Drinking Scale
SAE	Serious Adverse Events
SDU	Standard Drink Units
SNP	Single Nucleotide Polymorphisms
SSL	Secure Sockets Layer
TLFB	Time-Line Follow-Back
VAS	Visual Analogue Scale

2 Protocol Summary

Title:	The Effects of Exenatide, a GLP-1 Agonist, on Alcohol Self-Administration in Heavy Drinkers
Population:	The present study will involve 72 men and women aged 21 to 55 who exceed safe levels of drinking. Women and minorities who meet the study criteria will be eligible to participate. No vulnerable populations are being targeted for inclusion in this study
Intervention:	We propose to undertake a double-blind, randomized, placebo-controlled, crossover design trial that will test the effect of exenatide on alcohol self-administration and craving following a priming dose of alcohol. Subjects will receive either a 5 mcg dose of immediate release exenatide or a sham injection 30 minutes prior to completing a drinking challenge. Subjects will receive alcohol in the laboratory. Subjects will be presented with a priming drink mixed to raise their BAL 0.03 g/dl. Subjects will be presented with eight drinks, each mixed to raise their BAL 0.0125g/dl over a two-hour period. They will be told that they can either consume the desired number of drinks over the following 60 minutes or they will receive the equivalent in a cash reward. Subjects will serve as their own controls. The intervention will be repeated with a Sham injection/exenatide after a washout period.
Objectives:	The specific objective of this study is to test the effects of exenatide on alcohol self-administration and craving among heavy drinkers. This medication is a promising candidate that has unique actions on GLP-1 receptor systems that have been implicated in the regulation of alcohol consumption. Testing the effects of exenatide on drinking is a compelling opportunity that is consistent with the mission of NIAAA to evaluate the efficacy of re-purposed compounds with novel mechanisms that have the potential to treat AUD. If successful, this study could lead to a phase II randomized controlled trial to test exenatide as a treatment for AUD.
Design/Methodology:	This is a double-blind, randomized, placebo-controlled, crossover design trial that will test the effect of exenatide on alcohol self-administration and craving following a priming dose of alcohol. An established human laboratory self-administration procedure will be followed. Each subject will complete up to 4 clinic visits over a period of up to 38 days of participation. Study participation is comprised of a baseline assessment, alcohol self administration Trial 1, and alcohol self administration Trial 2. The volume of alcohol consumed during alcohol challenge trials 1 and 2 will be used to test the effect of exenatide on alcohol consumption. Craving measures (AUQ and VAS) collected during the self-administration trials will be used to test the effect of exenatide on alcohol craving.
Total Study Duration:	The entire study will take 24 months to complete.

Subject Participation Each subject's length of participation will be up to 38 days.
Duration:

3 Background/Rationale & Purpose

3.1 Background Information

Current models of care for treating Alcohol Use Disorder (AUD) include both behavioral therapies and pharmacotherapy¹. Although pharmacotherapy for AUD in the US has been available since 1948 when disulfiram was approved, options for treatment are limited as there are only four medications which have been approved by the FDA for treating AUD. Disulfiram, naltrexone, acamprosate, and long-acting naltrexone have all shown promise as agents to treat AUD² but no single medication has proven to be effective across the heterogeneous groups of people with AUD³. Movement towards models of personalized care and pharmacogenetic treatment matching⁴⁻⁵ hold some promise for improving AUD treatment outcomes, but the limited number of unique mechanisms of action of the currently approved drugs presents a challenge to implementing this model of care. Unfortunately, few novel compounds to treat AUD progress to phase II trials, and developing novel compounds is both costly and time-consuming⁶. One pathway of drug development efforts has been focused on re-purposing FDA approved medications that have promising mechanistic effects⁷ and some success has been achieved in using this strategy with anticonvulsants⁸. Identification of additional drugs with unique mechanisms of action that are found to reduce alcohol consumption could expand the treatment options and further the goal of personalized care for AUD. The overarching goal of our research is to identify agents with unique mechanisms that hold promise for treating AUD. The specific objective of this study is to determine whether exenatide, a GLP-1 receptor agonist that is FDA-approved for treating diabetes, has effects on alcohol craving and consumption.

Alcohol Use Disorder as a national health problem

More than 16 million adults suffer from Alcohol Use Disorder (AUD) in the United States⁸. The economic burden of this is estimated to be 249 billion dollars and approximately 88,000 Americans die from alcohol-related causes each year⁹. Untreated AUD is associated with an increased risk of accidents, injuries, suicide, and worsening of other health comorbidities¹⁰ and it is the fourth most preventable cause of death in the US⁹. Treating addiction more effectively has become a priority of national importance and the Surgeon General has urged researchers to undertake testing of new treatments to combat addiction¹¹. The present study is intended to answer the call for accelerating drug development for AUD by exploring the potential to re-purpose an existing drug as a treatment for AUD⁶⁻⁷.

Rationale for developing exenatide as an agent to treat AUD

GLP-1 is an endogenous peptide that regulates blood glucose by decreasing the rate of gastric emptying, promoting pancreatic beta cell activity if blood glucose levels are elevated, reducing glucagon release, and producing satiety for food¹³. Peptides that share structural similarities to GLP-1 have been synthesized including exenatide (synthetic Exendin-4) and liraglutide that are resistant to the GLP-1 metabolizing enzyme dipeptidyl peptidase IV¹³⁻¹⁴. There is now substantial preclinical evidence that these GLP-1 agonists can attenuate behaviors that model both the consumption and seeking of several commonly abused substances including alcohol^{7-8,10-11}, cocaine¹⁵, and nicotine¹⁶. Consistent with the idea that GLP-1 agonists are acting on overlapping pathways that regulate both food and drug intake, these compounds have been found to attenuate the reinforcing actions of food^{6,17-18}. Both Exendin-4 and liraglutide have been shown to reduce alcohol consumption by rodents^{7,8-11}. The administration of these drugs attenuates alcohol-induced place preference^{7,10} indicating that they reduce the rewarding effects of alcohol. Treatment with Exendin-4 blocks increases in

The Effects of Exenatide, a GLP-1 Agonist, on Alcohol Self-Administration in Heavy Drinkers
Version 1.8 10.5.20

alcohol intake following periods of alcohol deprivation, suggesting that this drug may decrease the likelihood of relapse during periods of abstinence¹⁹. Exendin-4 induced reductions in alcohol consumption were not observed in mutant mice who were missing central nervous system GLP-1 receptors, providing some evidence that the effects of this drug on alcohol consumption are specifically mediated by brain GLP-1 receptors¹¹. These effects in rodents may involve GLP-1 agonist attenuation of alcohol-induced release of mesolimbic dopamine, which is implicated in regulating the rewarding effects of alcohol^{7,10}.

The primary goal of this study is to determine whether findings from rodent studies of the inhibitory effects of GLP-1 agonists on behaviors related to alcohol consumption will translate into similar results in heavy drinking humans. In this proposed study we will examine the effects of the GLP-1 agonist exenatide on alcohol self-administration and cravings among heavy drinkers. Exenatide binds to the human GLP-1 receptor with an affinity equivalent to that of human GLP-1 peptide²⁰⁻²¹. This medication is approved for use in type 2 diabetes to help normalize blood glucose levels and has been tested in non-diabetic patients as a medication for the treatment of Parkinson's disease²². It should also be noted that the GLP-1 agonist liraglutide has received FDA approval as a medication for the promotion of weight loss²³.

At present, the most direct evidence implicating involvement of GLP-1 receptor systems in the regulation of alcohol consumption in humans is the finding that significant associations exist between select *GLP1-R* single nucleotide polymorphisms (SNP) and the occurrence of AUD²⁴. Suchankova et al. found that social drinkers who had the 168Ser/Ser variant for the rs6923761 SNP for the GLP-R1 gene consumed more alcohol in a self-administration task than subjects with the other variants of this SNP.

In the human brain, GLP-1 positive neurons have been found in the medullary tissue that contain the nucleus of the solitary tract (NTS)²⁵. This may be of significance because in rodents the NTS projects to key areas implicated in mediating food and alcohol reward including the ventral tegmental area and the nucleus accumbens²⁶⁻²⁹. GLP-1 receptor mRNA has been detected in mesolimbic regions of the primate (Rhesus monkey) brain³⁰. These findings suggest that exenatide may influence alcohol consumption in primates and, therefore possibly humans by acting through pathways that regulate drinking that are connected to the NTS. More evidence, however, is needed regarding the localization of GLP-1 neuron pathways within the human brain to support this hypothesis.

GLP-1 receptors, thus far, have been demonstrated to be present in several areas of the human brain including the hypothalamus, caudate-putamen, globus pallidus, temporal cortex, frontal cortex, parietal lobe, and orbitofrontal cortex³¹⁻³². Evidence concerning the functional consequences of acute administration of GLP-1 agonists, such as exenatide, on regional human brain activity has been presented in a few imaging studies. Injection of a 5 mcg dose of exenatide resulted in an increase in regional cerebral glucose metabolism in prediabetic subjects following glucose ingestion. This increase occurred in the overall mean in the collective regions that regulate glucose homeostasis (including frontal lobes, limbic system, insula, and putamen) and in those associated areas associated with food reward systems (including the orbital frontal cortex and anterior cingulate)³³. The acute intravenous administration of exenatide to obese subjects was found by one group of investigators to reduce the activation of brain structures including the amygdala, insula, orbitofrontal cortex, and putamen that were produced by the presentation of food related cues³⁴⁻³⁵. Other investigators have found that exenatide administration decreased the activation of brain structures (including the amygdala, insula, hippocampus, and frontal cortex) during food cue exposure in healthy obese subjects, but had no effect on these structures in lean subjects³⁶. These findings suggest that the acute administration of exenatide has effects on brain regions that have been shown to be associated with responses to alcohol cues (amygdala, temporal cortex, insula, anterior cingulate)³⁷⁻³⁹ and alcohol administration (amygdala, anterior cingulate; insula, orbital frontal

The Effects of Exenatide, a GLP-1 Agonist, on Alcohol Self-Administration in Heavy Drinkers
Version 1.8 10.5.20

cortex, putamen) in social and heavy drinkers⁴⁰⁻⁴¹. Given the demonstrated effects of exenatide on regional brain function associated with both food and alcohol reward, we expect that this drug will modulate alcohol craving and consumption.

This study will be conducted in compliance with the protocol, applicable regulatory requirements, and BMC/BU Medical Campus Human Research Protection policies and procedures.

3.2 Rationale and Purpose

This proposal holds significant innovation as there is strong evidence that medications that act as agonists at the GLP-1 receptor decrease alcohol consumption and its rewarding effects. There are currently no published clinical studies concerning the effects of GLP-1 agonists on alcohol consumption. This proposed study answers the call for accelerating the development of medications for AUD by testing a commercially-available and well-tolerated agent at a fraction of the cost of developing novel therapies. Currently there is one placebo controlled double-blind study of the effects of sustained release formulation of exenatide on alcohol consumption by alcohol dependent subjects (NCT03232112).

4 Objectives

4.1 Study Objectives

The specific objective of this proposal is to determine whether the GLP-1 agonist exenatide has effects on alcohol consumption and craving that identify it as a candidate medication for the treatment of AUD. This medication, which is approved by the FDA for the treatment of Type 2 diabetes, has been shown in preclinical studies to be a promising candidate as an AUD treatment medication because of its actions on GLP-1 receptor systems. These systems have been implicated in the regulation of alcohol consumption⁷⁻¹¹. Testing the effects of exenatide on drinking is a compelling opportunity that is consistent with the mission of NIAAA to evaluate the efficacy of re-purposed compounds with novel mechanisms that have the potential to treat AUD. If successful, this study would provide proof of concept that the administration of a GLP-1 agonist could reduce alcohol consumption in human subjects, and thereby provide support for the conduct of phase II randomized controlled trials to test one or more of the many currently FDA approved GLP-1 agonists as a treatment for AUD.

4.2 Study Outcome Measures

4.2.1 Primary Outcome Measures

The primary outcomes are alcohol consumption and cravings during the alcohol self-administration trials. Drinking volume during the alcohol self-administration will be measured to evaluate the effects of exenatide vs. sham injection on the rate of alcohol consumption after a priming drink. Alcohol craving will be measured using the Visual Analog Scale (VAS) and the Alcohol Urge Questionnaire (AUQ)³⁰ during the exenatide self-administration trial. These self-report measures of craving will be used to evaluate the effect of exenatide on craving vs. placebo.

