12.1 Study Hypotheses and Planned Analyses

For our primary outcomes, data from subjects who experience moderate to severe nausea during the alcohol self-administration trials will be excluded from our statistical analysis. Although the dosing chosen for this study minimizes the potential for nausea as a medication side effect, this may occur in some subjects. These subjects will be excluded from analyses as medication-induced nausea could confound the drinking outcomes. The presence of nausea will be established by a rating greater than 30 on a VAS scale that rates nausea from no nausea to unbearable nausea⁵³.

Hypothesis	Proposed Analyses
1. Subjects will consume less alcohol during an alcohol Challenge Trial when receiving exenatide	The volume of alcohol consumed during alcohol challenge trials 1 and 2 will be used to test the effect of exenatide on alcohol consumption. We will use a mixed

The Effects of Exenatide, a GLP-1 Agonist, on Alcohol Self-Administration in Heavy Drinkers
 Version 1.8 10.5.20

compared to when they receive a sham injection.	models repeated measures approach to test for differences between alcohol consumption between the exenatide and sham injection self-administration trials ⁵⁴⁻⁵⁵ . This data will be divided into first and second-hour blocks of self-administration. Within-subject factors for this analysis will include Treatment and Time Block. Trial order will be used as covariate in these analyses to allow evaluation as to whether the order of treatments had a significant effect on the outcome. Appropriate covariance structures will be determined using Akaike's information criteria to evaluate the best model fit. Results analysis will be examined for both treatment effects and the Treatment x Time Block interaction results.

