2. Subjects will report lower levels of craving as measured by the Visual Analog Scale (VAS) and the Alcohol Urge questionnaire (AUQ) during the exenatide Challenge Trial compared to the sham injection Challenge Trial.	Craving measures (AUQ and VAS) collected at 30-minute intervals during the self-administration trials will be used to test the effect of exenatide on alcohol craving. A mixed models approach will be used to test for differences in craving between the exenatide and sham injection Challenge Trials. Within-subject factors for this analysis will include Treatment and Time Block. Trial order will be used as covariate in these analyses to allow evaluation as to whether the order of treatments has a significant effect on the outcome.
Hypothesis 3: Areas under the breath alcohol concentration curves (AUC's) in heavy drinkers obtained during the first 40 minutes after ingestion of the priming drink of alcohol will be significantly lower in subjects when they receive exenatide as compared to when they are given sham injections	AUC's for BAC obtained using data obtained during the 40-minute absorption period will be compared between Challenge Trials using a repeated measures mixed models approach. In addition, individual BAC values obtained at 10-minute intervals after alcohol ingestion of the priming drink also will be compared between the sham injection and exenatide treatment trials using a repeated measures mixed models approach. A significant time x trial interaction value also will be taken to indicate a significant between trial difference in the rates of alcohol absorption.
Hypothesis 4. The proportion of subjects with post-trial blood glucose levels in the hypoglycemic range will not differ significantly between the sham injection and exenatide trials.	The proportion of subjects with blood glucose values below 50 mg/dl will be compared within subjects using the McNemar's test. We hypothesize that there will be no difference in blood glucose levels between the alcohol Challenge Trials.

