12.2 Sample Size Determination

A group size of 28 completers was selected for use in this study based on an assumed effect size of 0.7 suggested by similar alcohol self-administration studies with amount consumed as the primary outcome^{42,44}. This effect size is in the range we found for the anticonvulsant zonisamide used in a similar alcohol self-administration study⁴³. The sample size for this study is based on an estimated reduction of 1.5 standard drinks with an estimated standard deviation (2.1) of the between Challenge Trial differences in alcohol self-administration, with an effect size

The Effects of Exenatide, a GLP-1 Agonist, on Alcohol Self-Administration in Heavy Drinkers
Version 1.8 10.5.20

of this magnitude (i.e. 0.7). This requires a sample size of 28 to allow for detection of a significant within-subject difference in alcohol consumption with an alpha value of 0.01 and power value of 0.81. Based on an estimated 15-20% rate of non-completion for randomized subjects, we anticipate randomizing 36 subjects to achieve a sample of 28 completers. Given our experience with recruiting AUD populations into clinical trials, we expect a screening exclusion rate of roughly 50%. Approximately 72 subjects will be consented and screened in clinic to yield a sample of 36 eligible subjects.

Given that this a laboratory based experiment we do not plan to conduct any planned interim analyses in this study.

13 Ethics/Protection of Human Subjects

This study is to be conducted according to applicable US federal regulations and institutional policies (which are based in federal regulations, guidance, and ICH Good Clinical Practice guidelines).

This protocol and any amendments will be submitted to the Boston Medical Center and Boston University Medical Campus IRB, for formal approval of the study conduct. The decision of the IRB concerning the conduct of the study will be made in writing to the investigator. A copy of the initial IRB approval letter will be provided to the sponsor before commencement of this study.

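### Three primary measures and four written tests, with no lead outcome, testing order, multiplicity rule or stated significance level for the analyses

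*Combined protocol and SAP*

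**What the plan says.** - **Outcomes.** Section 4.2.1: "The primary outcomes are alcohol consumption and cravings during the alcohol self-administration trials". The same section gives VAS and AUQ as the craving instruments and ranks neither above the other.
- **Consumption tests.** Section 12.1, Hypothesis 1, fits a repeated-measures mixed model with treatment and hour block as within-subject factors and trial order as a covariate. It adds: "Results analysis will be examined for both treatment effects and the Treatment x Time Block interaction results".
- **Craving tests.** Section 12.1, Hypothesis 2: "A mixed models approach will be used to test for differences in craving between the exenatide and sham injection Challenge Trials". It also says "Within-subject factors for this analysis will include Treatment and Time Block", but mentions no interaction test for either scale.
- **Alpha.** The only significance level in the document is in Section 12.2, where 28 completers are said to suffice for "detection of a significant within-subject difference in alcohol consumption", "with an alpha value of 0.01 and power value of 0.81". That section does not present 0.01 as the level for the analyses in 12.1, nor as an allowance for several outcomes.
- **Interim analyses.** Sections 10.4 and 12.2 plan none, so no error is spent there.

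**The concern.** With three measures of equal standing and no decision rule, an analyst could report a significant result on any one of them as a positive primary outcome without departing from anything written. The analyst could also test at 0.05, because Section 12.1 sets no level. The sizing rests on one comparison of one outcome at 0.01. The analysis plan carries no such restriction, so the false-positive rate over the primary tests is left open. Section 4.1 intends the study to support a decision on phase II trials, so it matters that the decisive test be fixed in advance.

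**Working it through.** **1. Reproduce the plan's own figure.** Inputs from Section 12.2: effect size d = 0.7, n = 28 completers, alpha = 0.01. Sidedness is not stated; two-sided is tried first.

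The paired t-test has df = n − 1 = 27 and noncentrality d√n = 0.7 × √28 = 3.704. The two-sided 0.01 critical value is t = 2.771. Power from the noncentral t distribution is 0.815, and 28 is the smallest n that reaches 0.81. The stated 28 and 0.81 are reproduced. One-sided 0.01 would need only 24, so the plan's figure is a two-sided one. It covers a single comparison, consumption under exenatide against sham.

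**2. Count the tests in Section 12.1.**

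| Measure | Treatment effect | Treatment x Time Block |
|---|---|---|
| Consumption | written | written |
| AUQ | written | not written |
| VAS | written | not written |

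That gives four. The count would be six only if interactions were also tested for both craving scales. The plan names an interaction test where it wants one, under Hypothesis 1 and again for the breath-alcohol readings under Hypothesis 3, so its absence under Hypothesis 2 should not be filled in.

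**3. Chance of at least one two-sided false positive, independent tests.** Formula: 1 − (1 − a)^k, with all nulls true. The 0.05 level is an assumption; 0.01 is borrowed from Section 12.2.

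| Tests (k) | a = 0.05 | a = 0.01 |
|---|---|---|
| 3 (treatment effects only) | 1 − 0.95³ = 14.3% | 1 − 0.99³ = 3.0% |
| 4 (as written) | 1 − 0.95⁴ = 18.5% | 1 − 0.99⁴ = 3.9% |
| 6 (if craving interactions were added) | 1 − 0.95⁶ = 26.5% | 1 − 0.99⁶ = 5.9% |

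Whatever the correlation, four tests cannot exceed 4 × 0.05 = 20% or 4 × 0.01 = 4%.

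**4. Allow for correlation.** The documents give no correlations. The assumptions are 0.7 between AUQ and VAS, 0.3 between consumption and each craving scale, and independence of the interaction from the treatment effects. Simulating normal test statistics gives, for the four written tests, about 16.9% at 0.05 and 3.7% at 0.01. With a common correlation among the three measures running from 0.3 to 0.8, the four-test range is 17.9% down to 14.4% at 0.05, and 3.9% down to 3.2% at 0.01.

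**5. Favourable direction only.** Hypotheses 1 and 2 are directional. Each two-sided treatment test gives a false positive in the favourable direction with probability a/2. For the three treatment effects under independence this is 1 − 0.975³ = 7.3% at 0.05, or 1 − 0.995³ = 1.5% at 0.01, about half the two-sided rates.

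**6. What control would cost in power for consumption (n = 28, d = 0.7, two-sided).**

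| Rule | Level for consumption | Power |
|---|---|---|
| Consumption first, craving conditional | 0.01 | 0.815 |
| Holm over three treatment effects, total 0.05, first step | 0.05/3 = 0.0167 | 0.867 |
| Bonferroni over the four written tests, total 0.01 | 0.01/4 = 0.0025 | 0.643 |

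**The case against.** The best defence is that 0.01 is already strict. Applied to all four written tests, it holds the total at or below 4%, under a conventional 5%, and may have been chosen with several outcomes in mind. The arithmetic stands and limits the size of the problem. But Section 12.2 ties 0.01 to sizing the consumption comparison, and Section 12.1 does not adopt it, so it cannot be counted as a control rule.

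It can also be said that this is a small laboratory study, that its hypotheses are numbered and can be reported separately, and that Section 4.1 links proof of concept to reduced drinking. That makes consumption the natural lead outcome. But Section 4.1 also cites craving as grounds for calling exenatide a candidate, and Section 4.2.1 gives the two equal rank.

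Three stronger readings may tempt a reader, and the documents do not support them:

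- **Six tests, one main effect and one interaction per measure.** The interaction test is written for consumption only.
- **The trial can succeed by any of several routes.** No success rule is given, and a craving result or an interaction alone would not show the reduced drinking on which Section 4.1 rests proof of concept.
- **A planned 1% error rate is exceeded.** The 0.01 is the level of one test used for sizing; no trial-wide rate was ever set.

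**Conclusion.** The plan has three co-equal primary measures and four written tests, and leaves their joint false-positive rate uncontrolled. With all four nulls true, that rate is about 17% to 18.5% if each test is run at 0.05, and about 3.7% to 3.9% if each is run at 0.01. The lower ends rest on the assumed correlations (AUQ–VAS 0.7, consumption–craving 0.3, interaction independent) and the upper ends on independence. The 0.05 level is itself an assumption, since the plan states none. The gap is therefore material at 0.05 and modest at 0.01, and the plan does not say which applies. It should be corrected, and it does not undermine the design or the sample size.

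**What to change.** In Sections 4.2.1 and 12.1:

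1. Name the treatment main effect on total consumption over both blocks as the single primary test, at two-sided 0.01. This is the comparison sized in Section 12.2, and power stays at 0.815 with 28 completers.
2. Test the two craving scales only if consumption is significant, at the same level, either in an order the sponsor fixes before unblinding or with Holm across the two.
3. Label the Treatment x Time Block and trial-order results as supportive.

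**Cost.** Only protocol wording changes: no added subjects or visits, and no loss of power for consumption. The real price is that craving moves from co-primary to a conditional key outcome and can be claimed only after consumption is significant.

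**Alternative.** If the sponsor wants craving to stay co-primary, Holm across the three treatment effects at a total two-sided 0.05 also controls the error. Its first step of 0.0167 gives consumption power of about 0.87 at 28 completers. The price is a total error rate of 0.05 over the three effects, with consumption tested at a looser level than the 0.01 used for sizing.
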